9.3.2. Primary Endpoint(s)/Estimand(s) Analysis

Table 8. Primary Endpoint Analyses

Endpoint	Statistical Analysis Methods
Safety	
Descriptive statistics will be provided for each reactogenicity endpoint for each vaccine group. Local reactions (redness, swelling, and pain at the injection site) and systemic events (fever, nausea, fatigue, headache, vomiting, diarrhea, muscle pain, and joint pain) from Day 1 through Day 7 after vaccination will be presented by maximum severity and any severity. Descriptive summary statistics will include counts and percentages of participants with the indicated endpoint and the associated Clopper-Pearson 95% CIs (Section 9.3.1.1).AEs (including AESIs), NDCMCs, and SAEs will be categorized according to MedDRA terms. All AEs within 1 month after study intervention administration, and all AESIs, NDCMCs, and SAEs throughout the study will be descriptively summarized with counts, percentages, and associated Clopper-Pearson 95% CIs for each vaccine group (Section 9.3.1.1).A 3-tier approach will be used to summarize AEs. (1) Tier 1 events are prespecified events of clinical importance and are identified in a list in the product's safety review plan and described in detail in the SAP. (2) Tier 2 events are considered "relatively common" events; a MedDRA preferred term is defined as a Tier 2 event if at least 4 participants in at least 1 vaccine group report the event. (3) Tier 3 events are those that are neither Tier 1 nor Tier 2 events.

Table 8. Primary Endpoint Analyses

Endpoint	Statistical Analysis Methods
	
For Tier 1 and Tier 2 events, the 95% CIs for the difference in the percentage of participants reporting the events between the RSVpreF group and the placebo group will be calculated using the test statistic proposed by Miettinen and Nurminen. In addition, for Tier 1 events, the p-values will be presented for the difference between groups in the percentage of participants reporting the events. For Tier 3 events, counts and percentages for each vaccine group will be provided.
Immunogenicity	
GMTs and their associated 95% CIs will be descriptively summarized, by vaccine group, for both RSV A and RSV B at each blood sampling visit (Section 9.3.1.2.1).GMFRs of NTs from before vaccination to 1 month after vaccination will be descriptively summarized with 95% CIs, by vaccine group, for both RSV A and RSV B (Section 9.3.1.2.2).Empirical RCDCs will be provided for RSV A and RSV B NTs at 1 month after vaccination (Section 9.3.1.2.3).

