1.2. Schema

Table 1. Study Design

~360 Healthy adults ≥60 years of age randomized 2:1	Visit 1 (Day 1) Vaccination	Visit 2 1-Week Follow-Up Telephone Call 7-13 Days After Vaccination	Visit 3 1-Month Follow-Up Blood Draw 28-35 Days After Vaccination	Visit 4 2-Month Follow-Up Telephone Call 56-70 Days After Vaccination
Study Groups				
Group 1 RSVpreF n = 240	 			
Group 2 Placebo n = 120	 			
Safety				
Local reactions and systemic events ^a	Days 1 to 7 after vaccination			
AEs	Informed consent to Month 1			
AESIs SAEs NDCMCs	Informed consent to Month 2			
 Immunogenicity blood draw  Study intervention administration  Telephone contact for safety data				

a. Collected for 7 days, or longer for ongoing symptoms, after study intervention until symptom resolution.

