9.5. Sample Size Determination

As this study is not a hypothesis-testing study, the sample size was not based on study power for success.

It is expected that 240 participants will receive RSVpreF, with a total of 360 participants randomized in a 2:1 ratio. Assuming an ~10% non-evaluable rate, ~210 participants in the RSVpreF group will be assessed for immunogenicity.

Based on historical data, the GMFR at 1 month after vaccination with RSVpreF was ~10 (or 2.3 in the log e scale) among participants ≥ 60 years of age. With 210 participants expected to be evaluable after receiving RSVpreF, there is a 2.4% and 5% possibility of observing an LB of the 95% CI for the GMFR < 7.5 for RSV A and RSV B, respectively.

Antigen/ Strain	Common SD of Fold Rise (Log e Scale) ^a	Probability of Observing an LB of 95% CI for the GMFR < 7.5 (or 2.0 in the Log e Scale)
RSV A	1.1	2.4%
RSV B	1.2	5.0%

a. Based on Study C3671013.

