3.3. Other Safety Endpoint(s)

3.3.1. Adverse Events

AEs are classified into 1 of 3 tiers. Different analyses will be performed for different tiers (refer to [Section 6.3.1](#)).

- Tier 1 events: These are prespecified events of clinical importance and are maintained in a list in the product's safety review plan.

Guillain-Barré syndrome (from Day 1 through Day 43 after vaccination, where Day 1 is the vaccination day), atrial fibrillation (from Day 1 through the 1-month follow-up visit), and polyneuropathy (from Day 1 through Day 43 after vaccination, where Day 1 is the day of vaccination) have been identified as Tier 1 events for RSVpreF among the age group intended for this study. The RSV program Tier 1 list of MedDRA PTs is maintained by the safety risk lead in the CAETeLiSt and is referenced in the safety surveillance review plan for the program. The current list of Tier 1 events referenced by this study for RSVpreF should be confirmed to ensure that appropriate Tier 1 events will be used to produce final tables/graphs before conducting an analysis.

- Tier 2 events: These are events that are not Tier 1 but are “relatively common.” A MedDRA PT is defined as a Tier 2 event if at least 4 participants in at least 1 vaccine group report the event.
- Tier 3 events: These are events that are neither Tier 1 nor Tier 2 events.

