6.3. Other Safety Summaries and Analyses Endpoints

6.3.1. Adverse Events

For all of the AEs categorized in [Section 3.1.2.2](#), each individual AE will be categorized by MedDRA and descriptively summarized by vaccine group.

AEs are classified into 1 of 3 tiers ([Section 3.3.1](#)). For both Tier 1 and Tier 2 events, 2-sided 95% CIs for the difference between the vaccination group and placebo group in the percentage of participants reporting the events, based on the Miettinen and Nurminen² method, will be provided. In addition, for Tier 1 events, the p-values will also be presented for the difference between groups in the percentage of participants reporting the events. For Tier 3 events, counts and percentages for each vaccine group will be provided.

It should be recognized that most studies are not designed to reliably demonstrate a causal relationship between the use of a pharmaceutical product and an AE or a group of AEs. Except for select events in unique situations, studies do not employ formal adjudication procedures for the purpose of event classification. As such, safety analysis is generally considered an exploratory analysis and its purpose is to generate hypotheses for further investigation. The 3-tier approach facilitates this exploratory analysis.

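### With arms of 240 and 120, the Tier 2 rule of 4 reporters within one arm tilts the displayed point estimates toward RSVpreF for preferred terms with true rates of about 2% or lower

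*Protocol*

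**What the plan says.** Protocol 9.3.2 (Table 8) sets out a three-tier display of adverse events. A preferred term is "defined as a Tier 2 event if at least 4 participants in at least 1 vaccine group report the event". SAP 3.3.1 repeats the rule: "A MedDRA PT is defined as a Tier 2 event if at least 4 participants in at least 1 vaccine group report the event".

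Tier status decides whether the arms are formally compared. SAP 6.3.1 provides "For both Tier 1 and Tier 2 events, 2-sided 95% CIs for the difference between the vaccination group and placebo group", by the Miettinen-Nurminen method, and Protocol Table 8 agrees. P-values are reserved for Tier 1. For the remainder, Table 8 states: "For Tier 3 events, counts and percentages for each vaccine group will be provided".

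On arm sizes, Protocol 9.5 says: "It is expected that 240 participants will receive RSVpreF, with a total of 360 participants randomized in a 2:1 ratio". The schema in Protocol 1.2 gives "Group 2 Placebo n = 120". Neither document scales the count of 4 to arm size or comments on its effect under 2:1 allocation.

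**The concern.** A fixed count applied to arms of different size is a different percentage hurdle in each arm. A term at 4/240 and 2/120 (1.67% in both) receives a difference CI. A term at 3/240 and 3/120 (1.25% against 2.5%) does not. If low-rate terms enter the table chiefly because the larger arm's count ran high, the estimates shown are shifted toward RSVpreF by the selection itself.

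For preferred terms outside Tier 1, Tier 2 is the only between-group comparison planned. In a study without hypothesis tests, estimates and intervals are what the reader goes by. SAP 6.3.1 describes the tiered analysis as a way to generate hypotheses, and a tilt produced by the allocation ratio works against that purpose.

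**Working it through.** **Inputs.** Arms of 240 and 120 (Protocol 1.2 and 9.5; 240 + 120 = 360, which agrees with 2:1). Entry rule X ≥ 4 or Y ≥ 4, with X the RSVpreF count and Y the placebo count. The documents state no operating figure for this rule, so there is none to reproduce. They also give no preferred-term rates; the true rate p, equal in both arms, is an assumption shown over a range.

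**Method.** Exact enumeration with independent X ~ Bin(240, p) and Y ~ Bin(120, p).

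**Step 1, chance of entry at p = 1%.** P(X ≥ 4) = 22.1% and P(Y ≥ 4) = 3.3%. P(Tier 2) = 1 − (1 − 0.221)(1 − 0.033) = 24.6%. Of the terms that enter, 87% do so through RSVpreF alone, 10% through placebo alone and 3% through both.

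**Step 2, mean displayed difference at p = 1%.** Among selected terms the mean counts are 4.36 (RSVpreF) and 1.52 (placebo), against unselected expectations of 2.4 and 1.2. So 4.36/240 − 1.52/120 = 1.82% − 1.27% = +0.55 points, where the true value is 0.

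**Step 3, across rates (no true difference).**

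| True rate | Chance of Tier 2 | Entering via RSVpreF only | Mean displayed difference | RSVpreF higher / placebo higher |
|---|---|---|---|---|
| 0.5% | 3.6% | 91% | +0.92 points | 82% / 11% |
| 1% | 24.6% | 87% | +0.55 | 68% / 20% |
| 1.5% | 54% | 80% | +0.30 | 58% / 29% |
| 2% | 77% | 72% | +0.15 | 53% / 36% |
| 3% | 96% | 50% | +0.03 | 48% / 43% |
| 5% | nearly 100% | 14% | 0.00 | 48% / 46% |

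The remaining rows are ties. At 5% the split is the same as with no selection.

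**Step 4, an assumed mix of rates.** A whole table contains terms of many rates. With rates log-uniform from 0.1% to 5%, the lean is +0.15 points (53% / 38% of rows). From 0.1% to 2% it is +0.38 points (62% / 27%).

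**Step 5, do the intervals lean the same way?** No. Among selected null terms at 1%, 0.4% of Miettinen-Nurminen CIs lie wholly above zero and 5.0% wholly below; at 2%, 1.4% and 3.5%. For example, 4/240 against 0/120 enters with a CI of −1.5 to 4.2 points.

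**Step 6, the pooled rule X + Y ≥ 4.** With equal rates and a fixed total t, the expected RSVpreF count is t × 240/360 and the expected placebo count is t × 120/360. Both arm percentages then have mean t/360, so the mean difference is 0 for every t and every p. At 1% the split becomes 50% / 44%. The rule adds exactly six count pairs (RSVpreF, placebo): (1,3), (2,2), (2,3), (3,1), (3,2) and (3,3). In five of the six the placebo percentage is higher, which is how the lean is removed. None has a CI that excludes zero. The most extreme is (1,3): the difference is 0.42% − 2.50% = −2.08 points, the pooled proportion is 4/360 = 0.0111, and z = −0.0208 / √[0.0111 × 0.9889 × (1/240 + 1/120) × 360/359] = −1.78. The share of CIs below zero at 1% falls from 5.0% to 2.6% only because the table is longer (5.03% × 24.6% and 2.55% × 48.5% are both 1.24% of terms).

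**The case against.** A reader might infer three stronger things, and the documents support none of them.

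- *That a vaccine with no effect yields a table mostly showing RSVpreF excess, whatever the rates.* This holds only at about 2% and below, and barely at 2%. At 3%, 4 reporters is well under the expected 7.2, and almost every term enters regardless. The largest lean, at 0.5%, concerns terms that reach Tier 2 only about 4% of the time. The documents give no rates from which to say where most terms lie.
- *That the rule generates false harm signals.* Tier 2 status adds a CI, and null CIs that exclude zero fall more often on the placebo-higher side.
- *That placebo-excess terms disappear.* Tier 3 terms keep counts and percentages by arm; only the difference CI is lost. Low-rate terms with an RSVpreF excess often stay in Tier 3 too.

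Nor does a decision rest on the rule. Protocol 9.1 states that nothing is tested, Tier 2 carries no p-value, and SAP 6.3.1 calls safety analysis exploratory. The events of special interest are Tier 1 under SAP 3.3.1 and so escape the count. The any-AE estimand (SAP 2.2.1.2.2) does not depend on tiers. The lean also runs against the sponsor's product, so it does not hide harm.

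All of this stands, and it limits the point to presentation. What it leaves is that real differences of equal size are displayed unequally. With true rates of 2% on RSVpreF and 1% on placebo, a term reaches Tier 2 72% of the time; with the rates swapped, 39%.

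**Conclusion.** The point holds in a limited form. For preferred terms with true rates of about 2% or lower, selection into the difference-CI table runs mainly through the RSVpreF count. With no true difference, the point estimates shown then lean upward by about 0.15 points (at 2%) to 0.92 points (at 0.5%). From 3% up the effect is negligible. This rests on independent binomial counts, arms of exactly 240 and 120, and assumed background rates. It is a matter of which rows appear and how their estimates are centred; it does not affect the validity of the primary safety results. I would rate it as something to consider.

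**What to change.** In Protocol Table 8 and SAP 3.3.1, define a Tier 2 term as one reported by 4 or more participants in the RSVpreF and placebo groups taken together. Make the change before unblinding, so that the threshold is not chosen with counts by arm in view. Any term with 4 in one arm also has 4 in total, so no row that qualifies now is lost.

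The cost is one phrase in each document and a longer table with sparser rows. At a 1% rate a term's chance of display rises from 25% to 49%; at 0.5%, from about 4% to 11%. The threshold would correspond to 4/360 = 1.1% overall, a looser reading of what counts as relatively common.

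Lowering only the placebo threshold to 2, to equalise the percentages, is not a good substitute. It reverses the lean, to −0.30 points at 1%, with 35% of rows showing RSVpreF higher and 59% showing placebo higher.

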9.3.3. Secondary Endpoint(s)/Estimand(s) Analysis

Endpoint	Statistical Analysis Methods
Immunogenicity	
RSV A NT and RSV B NT seroresponse rate at 1 month after vaccination will be provided with the associated Clopper-Pearson 2-sided 95% CIs (Section 9.3.1.1).Immunogenicity data may be further summarized by age stratum.

9.3.4. Tertiary/Exploratory Endpoint(s) Analysis

Not applicable.

9.4. Interim Analyses

No interim analysis is planned. One final analysis will be performed when all immunogenicity and safety data are cleaned.

9.5. Sample Size Determination

As this study is not a hypothesis-testing study, the sample size was not based on study power for success.

It is expected that 240 participants will receive RSVpreF, with a total of 360 participants randomized in a 2:1 ratio. Assuming an ~10% non-evaluable rate, ~210 participants in the RSVpreF group will be assessed for immunogenicity.

Based on historical data, the GMFR at 1 month after vaccination with RSVpreF was ~10 (or 2.3 in the log e scale) among participants ≥ 60 years of age. With 210 participants expected to be evaluable after receiving RSVpreF, there is a 2.4% and 5% possibility of observing an LB of the 95% CI for the GMFR < 7.5 for RSV A and RSV B, respectively.

Antigen/ Strain	Common SD of Fold Rise (Log e Scale) ^a	Probability of Observing an LB of 95% CI for the GMFR < 7.5 (or 2.0 in the Log e Scale)
RSV A	1.1	2.4%
RSV B	1.2	5.0%

a. Based on Study C3671013.

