9.1. Statistical Hypotheses

This is a descriptive study without any hypothesis testing.

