9.3.1.2.2. Geometric Mean Fold Rises

Fold rises are defined as ratios of the results after vaccination to the results before vaccination. The calculations of fold rises are limited to participants with nonmissing values at both time points.

GMFRs will be calculated as the mean of the difference of logarithmically transformed assay results (later time point minus earlier time point) and exponentiating the mean. The associated 2-sided 95% CIs will be obtained by constructing CIs using the Student t distribution for the mean difference on the logarithm scale and exponentiating the confidence limits.

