5. GENERAL METHODOLOGY AND CONVENTIONS

5.1. Hypotheses and Decision Rules

There is no statistical hypothesis for the study.

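### Protocol 9.5: the stated 2.4% and 5.0% fit a GMFR bound of 7.39 (2.0 on the log e scale), not the 7.5 named beside them; for 7.5 the printed inputs give about 3.5% and 6.7%

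*Protocol*

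**What the plan says.** Protocol section 9.5 expects 240 participants to receive RSVpreF and about 210 of them to be evaluable for immunogenicity. From historical data it assumes that "the GMFR at 1 month after vaccination with RSVpreF was ~10 (or 2.3 in the log e scale"). The SDs of the log e fold rise are 1.1 for RSV A and 1.2 for RSV B, with the table footnote "Based on Study C3671013". From these it states that "there is a 2.4% and 5% possibility of observing an LB of the 95% CI for the GMFR < 7.5", where the first figure is RSV A and the second RSV B. The matching table column is headed "Probability of Observing an LB of 95% CI for the GMFR < 7.5 (or 2.0 in the Log e Scale") and lists 2.4% and 5.0%.

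The interval concerned is defined in protocol section 9.3.1.2.2, which obtains it by "constructing CIs using the Student t distribution for the mean difference on the logarithm scale". Section 9.3.1 makes it two-sided at the 95% level. On the role of these figures, section 9.5 says that "the sample size was not based on study power for success".

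**The concern.** The section gives the same bound in two forms that agree only to one decimal: 7.5 on the fold-rise scale and 2.0 on the log scale. The calculation depends on the gap between the assumed mean and the bound. That gap is 2.3026 − 2.0149 = 0.2877 for a GMFR of 10 and a bound of 7.5, but 2.3 − 2.0 = 0.3000 for the rounded logs. The probabilities lie in a tail and are reported to a tenth of a percentage point, so a difference of 0.012 in the gap can show at the printed precision.

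These two probabilities are the only operating characteristics offered with the sample size. If they belong to 7.39, a reader who takes the text at its word will think that falling below 7.5 is less likely than the printed inputs imply.

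**Working it through.** **Inputs, all from protocol section 9.5 unless noted**

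- n = 210 evaluable in the RSVpreF group
- Assumed GMFR about 10, also printed as 2.3 on the log e scale
- Bound 7.5, also printed as 2.0 on the log e scale
- SD of the log e fold rise: 1.1 (RSV A), 1.2 (RSV B)
- Two-sided 95% Student t interval on the log scale (sections 9.3.1 and 9.3.1.2.2)

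**Conversions**

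exp(2.0) = 7.389; ln 7.5 = 2.0149; exp(2.3) = 9.974; ln 10 = 2.3026.

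**Formula**

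The lower limit is LB = m − t(0.975, n − 1) × s/√n, where m and s are the sample mean and SD of the log fold rises. For true mean μ and log bound b,

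P(LB < b) = P(T′ < t(0.975, n − 1)),

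where T′ is noncentral t with n − 1 degrees of freedom and noncentrality (μ − b)/(SD/√n). Here t(0.975, 209) = 1.971, and SD/√210 is 0.0759 for RSV A and 0.0828 for RSV B.

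**Step 1: reproduce the stated figures.** With μ = 2.3 and b = 2.0, the noncentralities are 0.3000/0.0759 = 3.95 and 0.3000/0.0828 = 3.62. The probabilities are 2.42% and 4.99%, which match 2.4% and 5.0%.

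**Step 2: use the bound named in the text.** With μ = ln 10 and b = ln 7.5, the noncentralities are 0.2877/0.0759 = 3.79 and 0.2877/0.0828 = 3.47. The probabilities are 3.50% and 6.71%. A simulation of 400,000 trials gives 3.49% and 6.65%.

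**Step 3: separate the two roundings and vary n**

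| Mean μ | Bound b | n | RSV A (SD 1.1) | RSV B (SD 1.2) |
|---|---|---|---|---|
| 2.3 | 2.0 | 210 | 2.42% | 4.99% |
| ln 10 | 2.0 | 210 | 2.23% | 4.67% |
| 2.3 | ln 7.5 | 210 | 3.77% | 7.12% |
| ln 10 | ln 7.5 | 210 | 3.50% | 6.71% |
| ln 10 | ln 7.5 | 216 (240 × 0.9) | 3.10% | 6.09% |
| ln 10 | ln 7.5 | 240 | 1.90% | 4.10% |

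Only the first row gives the stated pair. It needs both rounded logs, the mean as well as the bound.

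**Step 4: could unrounded inputs explain the stated figures at 7.5?** At b = ln 7.5 and n = 210:

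- GMFR 10: the stated figures need SDs of about 1.054 (RSV A) and 1.151 (RSV B), which also print as 1.1 and 1.2.
- SDs exactly 1.1 and 1.2: they need a GMFR of about 10.12.
- GMFR 10 with SDs across their rounding ranges: RSV A runs from 2.3% (SD 1.05) to 5.0% (SD 1.15), and RSV B from 5.0% (SD 1.15) to 8.7% (SD 1.25).
- SDs exactly 1.1 and 1.2 with GMFR from 9.5 to 10.4 (values that print as about 10 and as 2.3): RSV A runs from 12.7% down to 1.0%, and RSV B from 18.9% down to 2.4%.

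**The case against.** The strongest reply is that nothing printed is wrong at its own precision. To one decimal, ln 7.5 is 2.0 and ln 10 is 2.3; the log bound stands next to 7.5 in the table header; and the printed log values reproduce both probabilities. The inputs are also openly approximate: the GMFR and the evaluable number are given as rough values, and the SDs to one decimal from another study. A GMFR of 10.1 with 214 evaluable participants and the printed SDs gives 2.4% and 4.9% at a true 7.5. Varying the GMFR (9.5 to 10.4) and the SDs together over their rounding ranges at n = 210 gives about 0.6% to 15.7% for RSV A and 1.6% to 22.1% for RSV B, so a shift of one or two points is small against the uncertainty in the inputs.

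Most of this stands. The shift is within the tolerance of the rounded inputs, and the documents do not show which values were used. With the GMFR fixed at 10 the stated figures sit at the low end of what the rounded SDs allow; once the GMFR also varies they do not, so no deliberate optimism should be read into them.

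It does not remove the point. The running text attaches the probabilities to 7.5 with no log value for the bound in that sentence. A reader who starts from a GMFR of 10, the printed SDs and n = 210 gets 3.5% and 6.7%. The values that would rescue the stated pair at 7.5 are not printed, whereas the rounded logs are printed and match both figures, so they are the simpler explanation.

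**Conclusion.** The concern holds as a minor arithmetic inconsistency. On the printed inputs, 2.4% and 5.0% correspond to a log mean of 2.3 and a log bound of 2.0, that is, a GMFR of 9.97 and a bound of 7.39. For the named bound of 7.5, the figures are 3.5% (RSV A, 1.1 points higher) and 6.7% (RSV B, 1.7 points higher). This assumes a GMFR of exactly 10, SDs of exactly 1.1 and 1.2, 210 evaluable participants and normally distributed log fold rises.

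The consequence is limited to the accuracy of this precision statement. Protocol section 9.1 says "This is a descriptive study without any hypothesis testing", and SAP section 5.1 says "There is no statistical hypothesis for the study". Neither document uses 7.5 as a success criterion, so no enrolment number, analysis or decision changes.

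**What to change.** Choose one of two repairs in protocol section 9.5:

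1. **Keep the bound at 7.5.** Recompute from the unrounded historical inputs, print ln 7.5 as 2.01 (2.0149), and state the GMFR, SDs and n that were used. If these are 10, 1.1 and 1.2, and 210, the probabilities become about 3.5% and 6.7%. Carry the unrounded log through the calculation: 2.01 with ln 10 gives 3.0% and 6.0%.
2. **Keep 2.4% and 5.0%.** State that they were obtained with log mean 2.3 and log bound 2.0, equivalent to a GMFR of 9.97 and a bound of 7.39. Simply relabelling the bound as 7.4 beside a GMFR of 10 comes close but gives 2.3% and 4.9%, so the log values should be named as the inputs.

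The cost is one sentence and one table header or column. Design, enrolment and analysis stay as they are.
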